## 1. Background

# 1.1. Non-Pharmacologic Interventions to Improve Blood Pressure Control

Despite the wide availability of multiple classes of antihypertensive agents, compelling data that blood pressure (BP) lowering reduces mortality and cardiovascular events, and decades of public health campaigns, half of American adults with hypertension do not achieve adequate BP control. Randomized controlled trials of interventions to improve BP control in patients with hypertension have largely focused on home blood pressure monitoring, nurse- or pharmacist-lead education and medication titration, and/or financial incentives. Though many of these interventions improve short-term blood pressure control, 4-10 they are cost-additive to health systems, 11 post-intervention data is mixed, 12,13 and none have been widely implemented.

Though consensus guidelines recommend dietary changes to improve hypertension control, with a particular recommendation in favor of the DASH (Dietary Approaches to Stop Hypertension) diet,  very few U.S. patients adhere to this complex dietary pattern.  The DASH diet reduced systolic BP (SBP) by 11 mmHg in randomized controlled trials in which participants were provided with food,  and 4 mmHg in a study testing a 6-month, 18-visit intensive lifestyle intervention intended to promote the DASH diet;  however, BP control was not sustained 12 months after the end of the intensive intervention. 

# 1.2. Effect of Intermittent Fasting on Metabolic Parameters

In contrast to the DASH diet, intermittent fasting (IF) is a dietary pattern that emphasizes temporal restriction of caloric intake rather than restricting the number of calories and/or changing the types of foods eaten. The simplest and most popular variation of IF involves restricting caloric intake to an 8-hour period each day, and consuming no calories for the other 16 hours (so-called 16:8 time-restricted feeding). In animal studies, IF has been shown to activate cellular pathways with potential disease-modifying benefits in a number of conditions. In small human studies, IF is associated with a reduction in SBP by 5-10 mmHg, LDL cholesterol by ~8 mg/dl, and weight by ~ 3 kg, though none of the studies of a time-restricted feeding regimen included concurrent controls. Some patients report that IF is easier to initiate and maintain than other dietary patterns, though this has not been tested empirically.

#### 1.3. Commitment Devices to Promote Healthy Behaviors

Commitment devices are centered in theoretical research that posits a planner-doer framework, wherein an individual can be conceptualized as dual sub-selves: The planner, who cares about long-term well-being; and the doer, who cares only for the present and prioritizes immediate payoffs. Conflict between the motivations and priorities of the planner and the doer sub-selves results in failure to follow-through with a plan when the moment to act arrives. Commitment devices are mechanisms by which the planner sub-self constrains the actions of their future doer sub-self by making certain choices more costly. Hard commitments impose a financial penalty for failing to follow through on the commitment, and soft commitments impose a psychological penalty. Hard commitments have been shown to change health behaviors, as in a study where smokers forfeited money deposited in a savings account if they failed to quit smoking after 6 months. However, monetary losses may not be attractive to many people, and effective soft commitment devices may be more appealing.

Pre-clinical research suggests that both intra- and interpersonal commitments might be useful components of a soft commitment device. Intrapersonal commitments have also been framed as implementation intentions, or specific plans as to where, how, and/or when an action will be taken. In small experiments, smokers who set a quit date were more likely to quit, and college students who set a date and time to visit a vaccination clinic were more likely to receive their vaccination. Interpersonal commitments leverage social networks, so that the penalty involves letting down a support partner. Involvement of social networks has been used to increase physical activity and improve control of weight and blood glucose in patients with obesity and diabetes. Social networks have been used explicitly within the context of commitment devices to encourage deposits in a savings account in a study of Chilean microentrepreneurs who either attended or did not attend a weekly peer support group meeting. Weight loss studies encouraging participants to exercise and change their eating behavior have employed commitment devices, including some that leveraged the involvement of family members or friends of the participant, with mixed results.

## 1.4 Rationale for the IFAST Study

The IF dietary pattern, though not inspired by behavioral economic concepts, is structured to take advantage of them and thus may be particularly amenable to a robust commitment device intervention. Changing one's eating patterns to a complex new diet is a cognitively intense process that requires active consideration of complex information multiple times per day, leading to cognitive overload and impaired decision-making. By contrast, IF, especially time-restricted feeding, is cognitively very simple. This simplicity may help participants avoid cognitive overload, initiate the dietary pattern and adhere over the long term.

This study seeks to test how a robust soft commitment device, incorporating both intra- and interpersonal commitments, affects uptake and adherence to an intermittent fasting dietary pattern, as compared with control, in patients with obesity and hypertension

# 2. Study Objectives

The objectives of this study are the following:

[figure not shown]
- 1. To determine the effect of a robust soft commitment device, incorporating both intra- and interpersonal commitments, on uptake and adherence to an intermittent fasting dietary pattern, as compared with control, in patients with hypertension and obesity
- 2. To determine the effect of the intervention promoting intermittent fasting on blood pressure and weight in patients with hypertension and obesity

# 3. Study Design

#### 3.1. General Overview

The IFAST study is a two-arm randomized controlled trial aimed at evaluating whether a soft commitment device increases uptake and adherence to an intermittent fasting dietary pattern compared with control in patients with hypertension and obesity. The study will randomize 34 patients with hypertension and obesity to a 12-week intervention employing a commitment pledge, involvement of a supportive partner, setting of implementation intentions, and multiple daily reminder text messages or to an attention control involving daily text messages alone.

Following the intervention, there will be a 6-week follow-up period (see study protocol figure below).

The study will be conducted using Way to Health, a research information technology platform at the University of Pennsylvania used previously for behavioral interventions.

After institutional review board (IRB) approval of the study, patients who meet the eligibility criteria will be approached in select cardiology clinics and invited to participate. Those who qualify and express interest will provide informed consent to the study procedures via the Way to Health platform. All patients will receive a blood pressure cuff and scale, which will be used to measure blood pressure and weight weekly. Within the Way to Health platform, patients will be randomized to the intervention or control arms. All other management decisions are completely at the discretion of the care providers. Data capture will include:

- **Baseline case report form** (for each patient) collecting clinical information abstracted from the medical record
- **Baseline survey** collected via the Way to Health platform including psychometric questions, dietary patterns, and experiences with weight loss and dieting
- Daily adherence to an intermittent fasting dietary pattern collected via self-report from text messages
- Weekly weight and blood pressure measurement collected via self-report from text messages

#### 3.2. Site

IFAST will enroll patients from cardiology clinics at the Hospital of the University of Pennsylvania and/or via email.

#### 3.3. Patient Selection Criteria

#### 3.3.1. Inclusion Criteria

Patients are eligible to be included in the study if they are  $\geq 18$  years of age and meet all of the following criteria:

- 1. Body mass index  $> 30 \text{ kg/m}^2$
- 2. Systolic blood pressure > 140 mmHg
- 3. Owns a smartphone or tablet operating the iOS or Android operating system

#### 3.3.2. Exclusion Criteria

Patients are excluded if they meet any of the following criteria:

- 1. Unable or unwilling to provide informed consent, including but not limited to cognitive or language barriers (reading or comprehension)
- 2. Type 1 diabetes
- 3. Use of insulin or insulin secretagogues (sulfonylureas, metaglinides)
- 4. Use of medications that require food intake
- 5. Ongoing use of pharmacologic therapy for weight loss
- 6. Self-reported eating disorder
- 7. Other medical condition that could be harmed by intermittent fasting as judged by study physician
- 8. Anticipated life expectancy less than 6 months
- 9. Any other reason why it is not feasible to complete the entire 6-month study

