#### 4.2. Baseline Questionnaire and Intermittent Fasting Education

After providing informed consent, participants will complete an online questionnaire. The baseline surveys will ask about dietary patterns and experiences with weight loss and dieting. Patients will also complete the Grit Scale and the MOS Social Support survey to obtain a psychometric profile relevant for persistence with a dietary intervention. They will also complete the 2005 Healthy Eating Index scale to assess pre-intervention diet quality.

Following completion of the baseline questionnaire, participants will receive education about intermittent fasting, including its definition, potential health benefits, and expectations about the experience.

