#### 4.3. Randomization

Once patients have received their scale and blood pressure cuff, they will be prompted by automated text message from the Way to Health platform to obtain a baseline weight and blood pressure. Once they provide baseline measurements and baseline questionnaires have been completed, they will be randomly assigned via the Way to Health platform to attention control or the soft commitment device using 1:1 allocation. Randomization will be stratified based on BMI ( $\leq$  and > 40 kg/m^2) and systolic blood pressure ( $\leq$  and > 160 mmHg) and will use blocks of 6 to ensure equal allocation over time.

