#### 5.2. Sample Size

With 34 patients (17 per arm), we will have 90% power to detect a 1 day per week difference in adherence to IF, assuming a standard deviation in days fasted per week < 1.24 The study will

have  $\sim 50\%$  power to detect a 10 mmHg change in systolic and diastolic blood pressure (assuming a standard deviation of 15 mmHg) and a 3 kg weight loss (assuming a standard deviation of 5 kg).

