#### 5.3. Data Analyses

Data for all patients who received at least 1 text message asking if they fasted the day prior, whether or not they completed all protocol requirements, will be included for analysis. Patient demographics, risk profiles, clinical characteristics, and baseline questionnaire results will be reported. All analyses will be performed using a modified intention-to-treat, excluding only patients who did not receive at least 1 text message asking if they fasted the day prior. Data can be missing for any day if the participant did not report adherence with daily fasting. For the main analysis, we will assume that days for which patients did not report adherence with daily fasting were non-adherent days. The primary analysis will compare days fasted per week between attention control and commitment device arms using a t test. Secondary analyses compare change from baseline in blood pressure and weight between arms using mixed effects regression models. Exploratory analyses will compare change from baseline in blood pressure and weight in patients who reported fasting  $\geq 4$  days/week versus those who reported fasting  $\leq 4$  days/week using mixed effects regression models.

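### Pre-study 16:8 fasting is neither screened for, specified as a baseline measure nor adjusted for, so any existing fasters would cost the primary comparison precision

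*Combined protocol and SAP*

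**What the plan says.** **Eligibility.** The exclusion list in section 3.3.2 ("Patients are excluded if they meet any of the following criteria") has nine items and the inclusion list in section 3.3.1 has three. The exclusions cover ongoing drug treatment for weight loss, but neither list mentions current or past time-restricted eating.

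**Baseline data.** Section 4.2 states: "The baseline surveys will ask about dietary patterns and experiences with weight loss and dieting". It adds the Grit Scale, a social support survey and the 2005 Healthy Eating Index. Fasting frequency is not named, and the questionnaire itself is not in the documents. The questionnaire comes before the fasting education, and section 4.3 requires it before randomisation.

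**Randomisation.** Section 4.3 assigns participants "to attention control or the soft commitment device using 1:1 allocation", stratified on BMI (cut at 40 kg/m²) and systolic pressure (cut at 160 mmHg).

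**Outcome and analysis.** Objective 1 concerns the effect of the device "on uptake and adherence to an intermittent fasting dietary pattern, as compared with control". Section 5.1 defines the primary outcome as adherence over 18 weeks in days per week, which is a level and not a change from baseline. Section 5.3 says: "The primary analysis will compare days fasted per week between attention control and commitment device arms using a t test". No covariate is named.

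**Sample size.** Section 5.2 says: "With 34 patients (17 per arm), we will have 90% power to detect a 1 day per week difference in adherence to IF", with the condition "assuming a standard deviation in days fasted per week < 1.24".

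**The concern.** The trial aims to start and sustain a behaviour that some recruits may already practise. Section 1.2 says of this regimen: "The simplest and most popular variation of IF involves restricting caloric intake to an 8-hour period each day". A person who already eats this way can pass every criterion, and may report many fasting days in either arm.

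Such participants could affect the primary comparison in two ways. They may respond less than new fasters, which shrinks the average difference. They also sit apart from new fasters on the outcome scale, which widens the spread within each arm. Eligibility, stratification and the t test all leave that spread in place. With 34 participants there is little room to absorb it, and an uneven split of a few existing fasters would move the estimate.

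**Working it through.** **1. The plan's own figure.** Inputs from section 5.2: 17 per arm and a difference of 1 day/week. The SD is printed as < 1.24. The 24 might be a citation number run into the text, so SD 1 is also tried. Alpha and sidedness are not stated; two-sided 5% is assumed. The noncentrality is d / (SD × √(2/17)), with √(2/17) = 0.343 and 32 degrees of freedom.

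- SD 1.0: 1/0.343 = 2.92, power 81%.
- SD 1.24: 1/(1.24 × 0.343) = 2.35, power 63%.

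Neither gives the stated 90%. SD 1.0 with a one-sided 5% test comes close (89%), and so does SD 1.24 with 34 per arm (91%). Two-sided 90% with 17 per arm needs an SD of about 0.87. This discrepancy is separate from the present point. The starting value used below is 81% (SD 1.0).

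**2. Model with a share p of prior fasters.** In each arm, new fasters have mean m and SD 1.0, and prior fasters have mean k and SD 0.5:

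- arm mean = (1 − p)m + pk
- arm variance = (1 − p) × 1.0² + p × 0.25 + p(1 − p)(k − m)²

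The two arm variances are averaged. Assumed, because the documents give none of these values: p = 10%; m = 3 or 4 in control and one day more with the device; k as listed in the table. With p = 0.10, the first two variance terms sum to 0.90 + 0.025 = 0.925.

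| Prior fasters (control / device) | New fasters (control / device) | Difference | Arm variances | SD | Power |
|---|---|---|---|---|---|
| none | any, +1 | 1.00 | 1.00 / 1.00 | 1.00 | 81% |
| 6.5 / 6.5 | 3 / 4 | 4.25 − 3.35 = 0.90 | 2.03 / 1.49 | 1.33 | 48% |
| 6.5 / 6.5 | 4 / 5 | 5.15 − 4.25 = 0.90 | 1.49 / 1.13 | 1.14 | 60% |
| 5 / 5.5 | 3 / 4 | 4.15 − 3.20 = 0.95 | 1.29 / 1.13 | 1.10 | 69% |
| 5 / 5.5 | 4 / 5 | 5.05 − 4.10 = 0.95 | 1.02 / 0.95 | 0.99 | 77% |

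For example, the control variance in the second row is 0.925 + 0.09 × 3.5² = 2.03.

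**3. Variations.**

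- With p = 5% and no response (k = 6.5), power is 62–70%.
- With SD 1.24, p = 10% and no response, power falls from 63% to 40–48%.
- If the planning SD already includes prior fasters, only dilution remains. At SD 1.0, power is 77% for p = 5% and 72% for p = 10%.

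**4. Chance imbalance.** With p = 10%, the probability that the arms differ by two or more prior fasters is about 38% (two independent binomials of size 17); with p = 5% it is about 21%. A split of 2 against 0 shifts the difference by (2/17) × 2.5 = 0.3 to (2/17) × 3.5 = 0.4 day, taking k = 6.5 and m = 4 or 3. This is the same variance already counted in step 2, not a further loss.

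**5. Adjustment.** By simulation with k = 6.5 and no response, adding a baseline fasting-days covariate recovers about 5 to 18 points of power at p = 5–10%. The gain depends on how well the recalled frequency predicts later behaviour. With no prior fasters the covariate costs about 1 point.

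**The case against.** The case against is substantial, and it removes several stronger readings that a reader might infer.

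- *Prior fasting is not measured.* The documents do not show this. The baseline survey asks about dietary patterns and dieting experience, and the instrument cannot be seen. What stands is that no fasting-frequency item is specified and no section uses one for eligibility, stratification or analysis.
- *An intermittent fasting study will fill with people already fasting.* Section 1.2 ranks 16:8 among variants of intermittent fasting; it gives no prevalence in patients with BMI above 30 and systolic pressure above 140. Recruitment is through clinics and a data pull of potentially eligible patients (section 4.1). Self-selection among those invited is possible but unquantified.
- *Prior fasters cannot respond.* The outcome is reported adherence over 18 weeks, and objective 1 covers adherence as well as uptake. Someone fasting fewer than seven days a week, or likely to lapse, can still benefit from reminders, a pledge and a partner. Unreported days count as non-adherent, so a prior faster who stops replying scores low. No response is therefore an unfavourable assumption, and the table shows a milder one.
- *The comparison is biased.* Randomisation prevents systematic imbalance in prior fasting between the arms.
- *Blood pressure and weight will not change in prior fasters.* This would need them to be at steady state, which no section states.

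The remaining argument is that, with size unknown, this is only a preference. That is partly fair. But the gap in the plan can be read directly from the text, and adjustment costs little even if no prior fasters enrol.

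**Conclusion.** The point holds as a weakness in precision. The plan has no provision for pre-study fasting at eligibility, stratification or analysis, and its outcome is a post-randomisation level that prior habit could influence strongly. In the 10% scenarios at SD 1.0 the loss runs from 4 points of power (81% to 77%) to 33 points (81% to 48%). The spread reflects how far prior fasters differ from new fasters and whether they respond to the device. Those inputs, the 10% share, and the alpha and sidedness are all assumptions. If nobody fasted beforehand, nothing is lost. The documents do not support a claim of bias, or any single figure for the damage.

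**What to change.** **Measure.** In the section 4.2 baseline questionnaire, specify an item asking on how many days per week, over the last 4 weeks, the participant went at least 16 hours without calories. The questionnaire already precedes the fasting education and randomisation, so the answer would be affected by neither.

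**Analyse.** In section 5.3, replace the primary t test with a linear model (ANCOVA) of days fasted per week on arm and that baseline value. Section 6.3 lets participants decline questions, so state in advance how a skipped answer is handled.

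**Cost.** One survey item and one degree of freedom, or about 1 point of power if there are no prior fasters.

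**Optional: exclusion.** Excluding regular fasters would sharpen the question about uptake but narrow the population. It would also turn away some volunteers; the batches of 500 and 1000 in section 4.1 count invitations, so they do not show how few. If exclusion is chosen, ask the question at eligibility screening. The questionnaire follows consent, and section 4.1 has devices mailed once consent is complete. Set a threshold for that purpose: the exploratory grouping in sections 5.1 and 5.3 is printed as ≥ 4 versus ≤ 4 days, so 4 falls in both groups, and it was not written as an eligibility rule.

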# 4. Study Procedures

#### 4.1. Screening and Informed Consent

Patients with body mass index  $> 30 \text{ kg/m}^2$  and SBP > 140 mmHg will be identified in select cardiology clinics and invited to participate. Interested participants will be instructed to visit the Way to Health platform online to register. They will also provide a contact number and email address, and will receive a reminder email and a phone call from a study coordinator for assistance with registration.

In addition, a data pull of potentially eligible participants will be performed during the study preparation phase. Once the research team obtains this eligibility list, the order of participants on the list will be randomized and then split into batches of 1000. The initial recruitment list will consist of 500 potentially eligible participants, which will help to ensure all the enrollment mechanisms are in place and working well. Three weeks after the initial recruitment emails/letters are sent, a second batch will be sent. Every 2-3 weeks thereafter, a new batch will be sent out until the randomization target is met. Interested participants will be provided with instructions to visit the Way to Health online platform to register for the study.

On the Way to Health platform, participants will learn more about the study, create an account, provide informed consent, and complete baseline study surveys. Study coordinators will be available to assist patients with this process, as necessary.

We will follow an IRB-approved approach taken by many studies using the Way to Health platform to obtaining informed consent. Upon reaching the portal, potential participants will be asked to create an account and will then be informed of the details of the study, including its objectives, duration, requirements, and financial payments. The Way to Health portal will then take interested participants through an online informed consent. The consent document will be divided into sections and potential participants will have to click a button to advance through each section. This is to help ensure that participants read the consent form thoroughly by breaking down the form into manageable blocks of text. Each section will have a button allowing the user to contact a researcher via email or by telephone if they have questions about the consent form. Successive screens will explain the voluntary nature of the study, the risks and benefits of participation, alternatives to participation, and that participants can withdraw from the study at any time. On the final consent screen, potential participants who click a clearly delineated button stating that they agree to participate in the study will be considered to have consented to enroll. Participants will be provided with details regarding how to contact the research team via email or phone at any time if they subsequently wish to withdraw from the study. This contact information will remain easily accessible via the participants' individual Way to Health web portal dashboards throughout the study.

Support partners will provide verbal informed consent via telephone for their name, email address, and phone number to be stored in the study database.

Once participants have completed the informed consent process, they will be mailed a scale and blood pressure cuff.

